3.6. Data Handling Conventions and Transformations

By-subject listings will be presented for all subjects in the Safety Analysis Set and sorted by subject ID number, visit date, and time (if applicable) unless otherwise specified. Data collected on log forms, such as AEs, will be presented in chronological order within subject.

Age (in years) on the date of the first dose of study drug and sex at birth will be used for analyses and presentation in listings.

If a subject was not dosed with study drug at all, then the date the informed consent was signed will be used instead of the first dose date of study drug. For some countries, only birth year is collected on the eCRF. In those cases, “01 January” will be used for the unknown birth day and month for the purpose of age calculation, unless age is captured on the eCRF.

Non-PK data that are continuous in nature but are less than the lower limit of quantitation or above the upper limit of quantitation will be imputed as follows:

- A value that is one unit less than the limit of quantitation will be used for calculation of descriptive statistics if the datum is reported in the form of “< x” (where x is considered the limit of quantitation). For example, if the values are reported as < 50 and < 5.0, values of 49 and 4.9, respectively, will be used for calculation of summary statistics. An exception for this rule is any value reported < 1. For the values reported as < 1 or < 0.1, value of 0.9 or 0.09 will be used for calculation of summary statistics.
- A value that is one unit above the limit of quantitation will be used for calculation of descriptive statistics if the datum is reported in the form of “> x” (where x is considered the limit of quantitation). Values with decimal points will follow the same logic as above.
- The limit of quantitation will be used for calculation of descriptive statistics if the datum is reported in the form of “≤ x” or “≥ x” (where x is considered the limit of quantitation).

The COBAS[®] AmpliPrep/COBAS[®] TaqMan[®] HCV Test, v2.0 for use with the High Pure System was used to determine HCV RNA results in this study. The lower limit of quantitation (LLOQ) of the assay is 15 IU/mL.

When the calculated HCV RNA value is within the linear range of the assay, then the result will be reported as the “<< numeric value>> IU/mL”. This result will be referred to in this document as the numeric result or as “≥ LLOQ detected” for categorical result.

When HCV RNA is not detected, the result is reported as “No HCV RNA detected” or “target not detected”. This result will be referred to in this document as “< LLOQ target not detected” or “< LLOQ TND”.

When the HCV RNA IU/mL is less than LLOQ of the assay, the result is reported as “< 15 IU/mL HCV RNA detected”. This result will be referred to in this document as “< LLOQ detected”.

The overall category of HCV RNA < LLOQ includes “< LLOQ TND” and “< LLOQ detected.”

For numerical HCV RNA data, values below LLOQ will be set to the LLOQ – 1 IU/mL (i.e. 14 HCV RNA IU/mL). HCV RNA values returned as “No HCV RNA detected” will also be set to 14 IU/mL.

If methods based on the assumption that the data are normally distributed are not adequate, analyses may be performed on transformed data (eg, log₁₀ scale) or nonparametric analysis methods may be used, as appropriate.

Natural logarithm transformation will be used for plasma/blood concentrations and analysis of PK parameters. Plasma concentration values that are below the lower limit of quantitation (BLQ) will be presented as “BLQ” in the concentration data listing. Values that are BLQ will be treated as 0 for determination of summary and order statistics and will be excluded in any calculation of geometric means or ratios.

For the presentation of summary and order statistics, if at least 1 subject has a concentration value of BLQ for the time point, then the minimum value will be displayed as “BLQ.” If more than 25% of the subjects have a concentration data value of BLQ for a given time point, then the minimum and Q1 values will be displayed as “BLQ.” If more than 50% of the subjects have a concentration data value of BLQ for a given time point, then the minimum, Q1, and median values will be displayed as “BLQ.” If more than 75% of the subjects have a concentration data value of BLQ for a given time point, then the minimum, Q1, median, and Q3 values will be displayed as “BLQ.” If all subjects have concentration data values of BLQ for a given time point, then all order statistics (minimum, Q1, median, Q3, and maximum) will be displayed as “BLQ.”

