### 9.1.3. Secondary Endpoints

For the PK Lead-in Phase, the secondary endpoints include antiviral activity measurements, including assessment of HCV RNA. AEs leading to permanent discontinuation of study drug(s) will be evaluated as a secondary safety endpoint.

For Treatment Phase, secondary efficacy endpoints include SVR4, SVR24, breakthrough and relapse. Additional efficacy evaluations may include HCV RNA change from Day 1; ALT normalization; viral kinetic parameters, and palatability of SOF oral granules. Secondary safety endpoints of growth and development measurements will be assessed (e.g. height, weight, and Tanner Stage Assessment).

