5. BASELINE CHARACTERISTICS

5.1. Demographics

Subject demographic variables (i.e. age, sex, race, and ethnicity) will be summarized by treatment group and total in each age group using descriptive statistics (n, mean, SD, median, Q1, Q3, minimum, and maximum) for age, and using the numbers and percentages of subjects for sex, race, and ethnicity. Age is calculated in years at the date of initial study drug administration. If a subject did not receive study drug after enrollment, the subject's age will be calculated from the date that the subject signed the informed consent form. The summary of demographic data will be provided for the Safety Analysis Set.

A by-subject demographic listing will be provided by subject ID number in ascending order.

In addition, demographic variables (i.e. age, sex, race, and ethnicity) will be summarized by treatment group defined in [Table 3-2](#) and total for 3 to < 6 years of age subjects.

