7.4. Body Weight, Height and BMI

An age- and sex-specific percentile will be derived for each weight, height and BMI measurement according to the downloadable SAS program available on the Centers for Disease Control (CDC) website using the year 2000 growth charts. Methods and SAS program published on the following CDC website will be applied to calculate the percentile {[Centers for Disease Control and Prevention \(CDC\) 2016a](#), [Centers for Disease Control and Prevention \(CDC\) 2016b](#)}.

Body weight, height, BMI and percentiles for body weight, height, BMI at each visit, and change from baseline at each visit will be summarized for the Safety Analysis Set using descriptive statistics (n, mean, SD, median, Q1, Q3, minimum, and maximum) by treatment group.

In the case of multiple values in an analysis window, data will be selected for analysis as described in Section 3.7.3 (Selection of Data in the Event of Multiple Records in a Window). No inferential statistics will be generated.

A by-subject listing of body weight, weight percentile, height, height percentile, BMI and BMI percentile will be provided by subject ID number and visit in chronological order.

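### Setting year-only birth dates to 01 January overstates exact age by about half a year when no eCRF age exists, and can bias absolute height and weight percentiles low

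*SAP*

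**What the plan says.** SAP 3.6 defines the analysis age: "Age (in years) on the date of the first dose of study drug and sex at birth will be used for analyses". SAP 5.1 repeats this for the demographics table: "Age is calculated in years at the date of initial study drug administration". Neither section says whether this is decimal age or completed years.

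SAP 3.6 then covers incomplete birth dates. "For some countries, only birth year is collected on the eCRF". For such subjects the SAP supplies a default, 01 January, which "will be used for the unknown birth day and month for the purpose of age calculation". The default gives way when the eCRF holds the age itself. The rule therefore reaches only subjects with a year-only birth date and no recorded age.

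SAP 7.4 uses age for growth: "An age- and sex-specific percentile will be derived for each weight, height and BMI measurement". On reporting, it says "Body weight, height, BMI and percentiles for body weight, height, BMI at each visit, and change from baseline at each visit will be summarized". The summaries are descriptive, without tests. Growth has formal standing in Protocol 9.1.3: "Secondary safety endpoints of growth and development measurements will be assessed".

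The SAP has no separate birth-date rule for the percentiles, no sensitivity analysis for imputed ages, and no count of the subjects concerned.

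**The concern.** A convention that always picks the earliest possible birthday errs in one direction only. In adults, half a year of age rarely matters. Here subjects are aged 3 to <18, and age is the index to the growth reference. A growing child compared with children half a year older looks shorter and lighter than he or she is. Protocol 1.1 itself raises the possible role of ribavirin in reducing growth rates, so percentiles that are low because of a date convention are unhelpful in the safety output meant to inform that question.

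The age summary is exposed as well. In completed years, a child correctly enrolled just below an age-group limit can be listed as having passed it.

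**Working it through.** The documents give no figure for the size of this error, so there is none to reproduce. The check is direct.

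**Inputs**
- Imputed birthday: 01 January (SAP 3.6); alternatives 01 July and 02 July.
- Births and first-dose dates spread evenly over the year (assumption).
- Height growth of 2 to 7 cm/year and a height SD at a given age of 4.5 to 7 cm (assumptions; the documents contain no growth-reference values).

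**1. Error in exact age.** Error = imputed age minus true age = (true birth day-of-year minus imputed day-of-year) / 365.25, averaged over 365 equally likely birth days.

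| Imputed date | Mean error | Range (years) | RMSE (years) |
|---|---|---|---|
| 01 January | +182 days = +0.498 year | 0 to +1.00 | 0.58 |
| 01 July | +1 day = +0.003 year | -0.50 to +0.50 | 0.29 |
| 02 July | 0 | -0.50 to +0.50 | 0.29 |

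With an assumed 10% seasonal swing in births, the means are +0.503 year (01 January) and +0.005 year (02 July), so uniformity is not critical.

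**2. Error in completed years.** Let d be the first-dose date and b the birthday, both as fractions of the year.
- 01 January: imputed age is one year too high whenever b falls after d. The probability is 1/2, so about 50% are wrong and the mean error is +0.50 year.
- Mid-year: imputed age is wrong when d lies between b and mid-year. The probability is the mean of |d - 0.5| = 0.25. Errors in the two directions balance, so the mean is 0.

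**3. Height percentile, if exact age is used.** Shift in z = -(0.5 x yearly growth) / SD; the percentile of a true median child is Phi(shift).
- 2 cm/year, SD 7 cm: -0.5 x 2 / 7 = -0.14, 44th percentile.
- 5 cm/year, SD 7 cm: -0.5 x 5 / 7 = -0.36, 36th percentile.
- 5 cm/year, SD 5 cm: -0.5 x 5 / 5 = -0.50, 31st percentile.
- 7 cm/year, SD 4.5 cm: -0.5 x 7 / 4.5 = -0.78, 22nd percentile.
- No growth: shift 0, 50th percentile.

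For a group whose true mean percentile is 50, with the error spread over 0 to 1 year, the mean percentile falls to about 46 (2 cm/year, SD 7 cm) or 30 (7 cm/year, SD 4.5 cm). With a mid-year date it stays at about 50.

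**4. Which age enters the percentile program.** SAP 7.4 does not say. If completed years were used, 01 January gives the calendar-year difference, while exact age is that difference plus (d - b). Since d - b averages 0, the mean error against exact age is 0. Mid-year subtracts one year whenever d precedes mid-year, probability 1/2, so its mean error is about -0.5 year. The advantage in step 3 therefore depends on exact age being used.

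**The case against.** The case against making much of this is substantial.

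- **Scope.** The exception for a recorded age is part of the rule, and Protocol 10.1.4 allows a date of birth on forms sent to the sponsor, so year-only dates look like a country exception. A reader might infer that every subject from such a country is affected. The documents do not support that, and the effect on a group summary could be negligible. This stands. The exception does not settle everything, however: a recorded entry age gives no birth date, and SAP 7.4 needs an age for each measurement.
- **The link to percentiles is inferred.** SAP 3.6 speaks of age at first dose, and SAP 7.4 names no age input. With completed years, a mid-year date alone would introduce a bias. This stands as a condition, and it is why the age input has to be specified together with the date.
- **Size.** It is tempting to quote only the figures for fast growth. About half the sample is aged 12 to <18 (SAP 1.2), where growth may be slow or finished. At 2 cm/year, with the same SDs, a median child reads at the 41st to 44th percentile.
- **Direction.** A reader might infer that all growth percentiles fall. That follows for height and weight during growth. The documents do not give the BMI reference curve, so the direction for BMI is not established.
- **Consequence.** The same date error applies at baseline and later visits, so it largely cancels in change from baseline, and the outputs are descriptive. A reader might infer that imputed age moves subjects between the groups tested for SVR12. It does not, because SAP 3.2 groups the FAS as enrolled.

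What survives is a one-directional error, by construction, in the reported age and potentially in absolute height and weight percentiles.

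**Conclusion.** The point holds, as a minor one. For year-only subjects without an eCRF age, 01 January overstates exact age by about 0.5 year on average, assuming births spread roughly evenly over the year. Completed-year age is one year too high in about half of them.

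The effect on percentiles is conditional on exact age being computed from the imputed date. The range of the 22nd to 44th percentile for the height of a median growing child rests on the assumed growth rates and SDs, and falls to no shift when growth has ended. The effect on weight percentiles has the same direction during growth but has not been sized. The effect on any group summary cannot be sized, because the number of affected subjects is not given. No efficacy conclusion is at risk.

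**What to change.** In SAP 3.6, replace 01 January by a mid-year date (01 or 02 July). Where the eCRF age or the enrolled age group narrows the possible birth dates, use the midpoint of the remaining interval. When completed-year age is known, that midpoint has an RMSE of about 0.20 year, against 0.25 year for 01 July moved to the nearest admissible date.

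In SAP 7.4, state that percentiles use decimal age, or age in months, at each measurement date. This must accompany the new date, for the reason in step 4. Report how many subjects had an imputed birth date, by treatment group.

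The cost is a few sentences and a small amount of programming; the interval midpoint is slightly more than a changed constant. No new data are needed. The change removes the average bias but not individual error: up to about 6 months either way remains.

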**Study Design:**

Open-label, multi-cohort, two-part study evaluating the PK, safety, and antiviral activity of SOF in chronic HCV-infected pediatric subjects.

The study will be divided into 2 parts as follows:

**PK Lead-in:** Will evaluate and/or confirm age appropriate SOF doses by analyzing PK, safety, and antiviral activity of SOF administered in combination with RBV through 7 days of dosing for each of three cohorts. Children aged 3 to < 6, children aged 6 to < 12 years and adolescents aged 12 to < 18 years with genotype GT-2 or GT-3 HCV infection and evidence of HCV RNA  $\geq$  1000 IU/mL at study entry will be evaluated. Subjects must be treatment naïve to participate in the PK Lead-in Phase.

Three cohorts of up to 10 subjects each will be sequentially enrolled:

- Cohort 1: 12 to < 18 years old weighing  $\geq$  45kg
- Cohort 2: 6 to < 12 years old weighing  $\geq$  17kg and < 45kg
- Cohort 3: 3 to < 6 years old

The study will start with Cohort 1. Subjects will receive SOF (400 mg adult tablet or 4 x 100 mg tablets if determined necessary based on SOF swallowability assessment) + RBV for 7 days with intensive PK conducted on Day 7. Cohort 2 subjects will receive 200 mg SOF (2 x 100 mg tablets or 4 x 50 mg capsules containing granules if determined necessary based on the SOF swallowability assessment) + RBV for 7 days with intensive PK conducted on Day 7. Cohort 3 subjects weighing  $\geq 17$ kg will receive 200 mg SOF (4 x 50 mg capsules containing granules) + RBV for 7 days with intensive PK conducted on Day 7. Cohort 3 subjects weighing  $< 17$ kg will receive 150 mg SOF (3 x 50mg capsules containing granules) + RBV for 7 days with intensive PK conducted on Day 7.

PK Lead-in subjects in each cohort (Cohorts 1, 2 and 3) will immediately enroll in the Treatment Phase as they complete Day 7 of the PK Lead-in Phase. They will continue dosing with SOF + RBV with no interruption of study drug administration. Subjects rolling over from the PK Lead-in will not be required to perform screening, Day 1 or Week 1 visits in the Treatment Phase.

Following completion of study treatment in the PK Lead-in of each Cohort, intensive PK and safety results will be reviewed to confirm the appropriateness of the evaluated SOF dose for the Treatment Phase of that Cohort as well as to determine the age-appropriate dose to be evaluated in the PK Lead-in of the next Cohort.

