**Evaluation Criteria:**

- Safety:** AEs, laboratory tests, physical examination, vital signs and Tanner Pubertal Stage assessments will be collected throughout the study.
- Efficacy:** Efficacy will be evaluated using scheduled assessments of HCV RNA performed using COBAS® AmpliPrep/COBAS® TaqMan® HCV Test.
- PK:** For subjects in the PK Lead-in, steady-state PK of SOF and its major metabolites GS-566500 and GS-331007 will be assessed at Day 7. For Cohorts 1 and 2, plasma samples will be collected for PK analyses following dosing of study drugs on Day 7 at the following time points: 0 (predose), 0.5, 1, 2, 3, 4, 8, and 12 hours postdose (with predose also serving as t= 24). For Cohort 3, plasma samples for PK analyses will be collected at the following time points: 0 (predose), 2, 4, 8, and 12 hours postdose (with predose also serving as t = 24). Plasma PK parameters such as Cmax, Tmax, Clast, Tlast, Ctau, AUCtau, and t1/2 will be estimated. For all subjects in the Treatment Phase, a single PK blood sample will be collected at all visits while on treatment. The PK of SOF, GS-566500 and GS-331007 and/or ribavirin will be assessed. The effect of age and SOF dose on PK (SOF and GS-331007) will be explored.

---

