ICH	International Conference on Harmonization (of Technical Requirements for Registration of Pharmaceuticals for Human Use)
LLT	lower level term
LLOQ	lower limit of quantitation
MedDRA	Medical Dictionary for Regulatory Activities
PK	pharmacokinetics
PT	preferred term
Q1	first quartile
Q3	third quartile
RBV	ribavirin
RNA	ribonucleic acid
SAE	serious adverse event
SAP	statistical analysis plan
SI (units)	International system of units
SOC	system organ class
SOF	Sofosbuvir (GS-7977)
SVR	sustained virologic response
SVRx	sustained virologic response x weeks after stopping study drug
TEAE	treatment-emergent adverse events

TFLs	tables, figures, and listings
ULN	upper limit of normal
WBC	white blood cell
WHO	World Health Organization

PHARMACOKINETIC ABBREVIATIONS AND DEFINITIONS

λ_z	terminal elimination rate constant, estimated by linear regression of the terminal elimination phase of the log plasma/serum concentration versus time curve of the drug
AUC	area under the plasma/serum concentration versus time curve
AUC _{tau}	area under the plasma/serum concentration versus time curve over the dosing interval
CL	systemic clearance of the drug after intravenous administration
CL/F	apparent oral clearance after administration of the drug: CL/F = Dose/AUC _{inf} , where “Dose” is the dose of the drug
C _{max}	maximum observed plasma/serum concentration of drug
C _{tau}	observed drug concentration at the end of the dosing interval
E _{max}	maximum (pharmacodynamic) effect
t _{1/2}	estimate of the terminal elimination half-life of the drug in serum/plasma, calculated by dividing the natural log of 2 by the terminal elimination rate constant (λ_z)
T _{max}	time (observed time point) of C _{max}

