8. PHARMACOKINETIC ANALYSES

8.1. PK Analysis in PK Lead-in Phase (Intensive PK Analysis)

Intensive PK Analysis will be performed using PK Lead-in Phase Intensive PK Analysis Set. Concentrations of SOF and GS-331007 from subjects in the PK lead-in Phase over sampling time will be listed and summarized using descriptive statistics (n, arithmetic mean, geometric mean and its 95% confidence interval, coefficient of variation [%CV], SD, median, Q1, Q3, minimum, and maximum) by nominal time and cohort. For Cohorts 1 and 2, plasma samples will be collected for PK analyses following dosing of study drugs on Day 7 at the following time points: 0 (predose), 0.5, 1, 2, 3, 4, 8, and 12 hours postdose. For Cohort 3, plasma samples for PK analyses will be collected at the following time points: 0 (predose), 2, 4, 8, and 12 hours postdose. PK parameters from subjects in the PK lead-in Phase will be summarized (e.g; AUC_{τ} , AUC_{last} , C_{max} , T_{max} , C_{last} , T_{last} , C_{τ} , $T_{1/2}$, volume of distribution and clearance, as appropriate) by cohort.

To confirm the appropriateness of SOF dose for each age group, PK parameters for GS-331007 will be compared between each age group from this study and the SOF NDA patient population (which includes population-PK derived PK exposure data from adult phase 2 and 3 studies) by carrying out an analysis of variance (ANOVA) for log-transformed AUC_{τ} of GS-331007 as the primary endpoint and C_{max} of GS-331007 as a secondary endpoint. Geometric Mean Ratio and its 90% confidence interval will be provided.

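### Dropping BLQ values from geometric means, with no cut-off and no % BLQ shown, makes late-time SOF geometric means describe detectable samples only

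*SAP*

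**What the plan says.** SAP 3.6 handles BLQ plasma concentrations in two ways. For arithmetic and order statistics: "Values that are BLQ will be treated as 0 for determination of summary and order statistics". For geometric means and ratios, the same values "will be excluded in any calculation of geometric means or ratios". Protocol 9.2.2 has the same pair of rules.

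SAP 3.6 also sets display rules by BLQ share, but only for order statistics. Above 25% BLQ, the minimum and Q1 print as BLQ. Above 50%, "then the minimum, Q1, and median values will be displayed as" BLQ, and above 75% Q3 joins them. The geometric mean has no such threshold, no separate n and no accompanying % BLQ.

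The rule applies to SOF through SAP 8.1: "Concentrations of SOF and GS-331007 from subjects in the PK lead-in Phase over sampling time will be listed and summarized using descriptive statistics", by nominal time and cohort, and the list of statistics includes the "geometric mean and its 95% confidence interval". Protocol 9.4 lists the geometric mean for PK parameters, Ctau among them. The SAP defines Ctau as the "observed drug concentration at the end of the dosing interval", so a BLQ observation makes Ctau BLQ. The protocol synopsis (Evaluation Criteria) takes the Day 7 predose sample for this, "with predose also serving as" the 24 h value. On cohort size the synopsis says: "Three cohorts of up to 10 subjects each will be sequentially enrolled".

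**The concern.** One table row would mix two populations: an arithmetic mean over all subjects with BLQ as 0, and a geometric mean with its CI over detectable subjects only. A geometric mean of detectable values cannot fall below the assay limit, however low the true one is. When more than half the values are BLQ, the row prints the median as BLQ beside a numeric geometric mean above the limit. If concentrations are lognormal, the true geometric mean equals the true median, so the printed figure is on the wrong side of the limit.

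This matters most where BLQ values are common. The plan gives no SOF half-life, but its own exposure table suggests that SOF is low by 8 to 12 h. At stake is the accuracy of the descriptive late-time SOF rows, and possibly a Ctau row resting on one or two unusual subjects.

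**Working it through.** The documents state no BLQ fraction, SOF half-life, plasma assay limit (LLOQ) or SOF Ctau, so there is no plan figure to reproduce.

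**1. Inconsistency without any kinetic assumption.** Take 10 subjects at one time point, 8 of them BLQ, with detected values 10 and 12.
- Arithmetic mean, BLQ as 0: (10 + 12)/10 = 2.2.
- Geometric mean, BLQ dropped: √(10 × 12) = 10.95.

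A geometric mean cannot exceed the arithmetic mean of the same values; here the two use different values.

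**2. How fast SOF falls.** Inputs are the means (%CV) in Protocol Table 1-2. For Cohort 1, AUCtau is 1170 and Cmax 592 (84.1%). For Cohort 2, AUCtau is 977 and Cmax 635 (50.9%).
- AUCtau/Cmax: 1170/592 = 1.98 h; 977/635 = 1.54 h.
- If decline is mono-exponential, ln 2 × ratio is roughly a ceiling on half-life: 1.37 h and 1.07 h.
- C(t) = Cmax × exp(−t × Cmax/AUCtau) gives about 10 and 3.5 ng/mL at 8 h, 1.4 and 0.3 ng/mL at 12 h, and essentially nothing at 24 h.

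These are ratios of group means, and Cohort 2 includes two subjects scaled from 400 mg to 200 mg. The table has no Cohort 3 data.

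**3. Inflation at a given BLQ share f.** For lognormal values, the detectable-only geometric mean divided by the true one is exp[s·φ(z)/(1 − f)], with s = √ln(1 + CV²) and z the f-quantile of the standard normal. The CVs of 50.9% and 84.1% give s = 0.48 and 0.73.

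| BLQ share | 10% | 25% | 50% | 75% | 90% |
|---|---|---|---|---|---|
| Inflation | 1.10–1.15 | 1.2–1.4 | 1.5–1.8 | 1.8–2.5 | 2.3–3.6 |

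At the tabulated CVs the factor stays below 2 until more than half the samples are BLQ. Wider late-time variability raises it.

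**4. Inflation by sampling time.** Assumptions: LLOQ 1 to 10 ng/mL, mono-exponential decline from 1 h at the half-life ceiling, Table 1-2 Cmax and CV, and a between-subject SD on the elimination rate of 0 or 20%.

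Worked case (Cohort 1, 12 h, LLOQ 1, SD 0):
- Geometric mean Cmax = 592/√(1 + 0.841²) = 453; at 12 h, 453 × exp(−11/1.98) ≈ 1.73.
- z = ln(1/1.73)/0.731 = −0.75, so f ≈ 0.23.
- Inflation = exp(0.731 × 0.301/0.774) ≈ 1.3.

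Simulation with 20% SD, LLOQ 1 to 10:

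| Time | Cohort 1: % BLQ, inflation | Cohort 2: % BLQ, inflation |
|---|---|---|
| 8 h | 1–41%, 1.0–2.0 | 6–71%, 1.2–3.2 |
| 12 h | 35–93%, 2.2–10.6 | 72–99%, 5.7–36 |

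At 4 h the factor is about 1.0 throughout. With SD 0, the 12 h range in Cohort 1 is 1.3 to 7.4. In Cohort 2 it is 2.7 at LLOQ 1, with virtually no detectable sample at 5 or 10.

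**5. Predose and Ctau.** At the half-life ceiling, even with a 30% spread on the rate, 98 to 100% of 24 h values are BLQ. The chance that all 10 subjects are BLQ is then at least 0.98^10 = 0.82, and usually no geometric mean exists.

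**The case against.** The strongest reply is that this is a consistent, prespecified convention in tables that decide nothing, and that readers are warned because the median and quartiles print as BLQ and individual BLQ values are listed as such. That stands as far as it goes. But the warning applies to the order statistics, and nothing marks the geometric mean or its CI as resting on a subset.

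Several stronger readings are tempting, and the documents do not support them:
- **All SOF geometric means are several-fold too high.** Early and peak times are hardly touched, and 8 h gives 1.0 to 3.2. The 12 h figure depends on an unstated spread in elimination: at LLOQ 1, removing the 20% SD lowers it from 2.2 to 1.3 (Cohort 1) and from 5.7 to 2.7 (Cohort 2).
- **The 36-fold figure would be seen.** It arises at about 99.4% BLQ, where the chance that none of 10 subjects is detectable is 0.994^10 ≈ 0.94.
- **Ctau is biased several-fold.** It is usually not calculable, and SAP 8.1 gives its parameter list as examples, as appropriate.
- **The plotted terminal profile is flattened.** Protocol 9.4 plots arithmetic means and medians; no geometric mean profile is planned.
- **The age and dose exploration is distorted.** No section bases it on late-time SOF geometric means, and SAP 8.2 models SOF by population PK.

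**Conclusion.** The point holds as a minor defect in descriptive reporting. Followed as written, the rule makes late-time SOF geometric means conditional on detection, biased upward, and able to exceed the arithmetic mean in the same row. That inconsistency needs no assumption about the drug. The size does: it rests on the assumed LLOQ, the assumed spread in elimination rate and mono-exponential decline. The ranges in the working are therefore indicative, not findings from the documents.

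A reader might infer that dose confirmation is at risk. It is not: SAP 8.1 compares GS-331007 AUCtau (primary) and Cmax (secondary) with adults, and neither depends on late-time SOF geometric means.

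**What to change.** In SAP 3.6, with a cross-reference in 8.1:
- Show the number of values used and the % BLQ beside every geometric mean of concentration or Ctau.
- Where more than 50% of values at a time point (or for Ctau) are BLQ, display the geometric mean and its CI as not calculated, matching the existing threshold for the median.
- Optionally, add a lognormal estimate that treats BLQ as left-censored. With up to 10 subjects per cohort it leans on the distributional assumption, so it should supplement the table and not replace the rule.

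The cost is a few sentences of SAP text and minor table programming. The downside is that some late-time SOF geometric means, and most likely SOF Ctau, will be blank.
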